Primary registry and	ISRCTN registry. Registration number tbc
trial number	
Countries of	England
recruitment	
Research Sites	(1) Doncaster Metropolitan Borough Council
	(2) Bradford Metropolitan Borough Council
	(3) London Borough of Tower Hamlets Council
	To undertake a pilot study in order to inform the design
	and conduct of a main trial to evaluate the impact of the
Aims	intervention on a range of interconnected challenges for
-	UK public health nutrition in areas of high deprivation
	and low fruit and vegetable consumption.
	Fresh Street a weekly voucher scheme for fresh FV with
	vegetable-based recipes, brief nutritional information &
	healthy eating and health-related behaviour change
Intervention	information delivered to all households in an area; all
	households are eligible, regardless of size, type or
	income. Vouchers are redeemable with local
	independent FV retailers.
Inclusion criteria	High deprivation (IMD deciles 1-4)
(clusters)	Below average FV consumption
· · · ·	
Methodology/ Study	Pilot RCT with process evaluation.
design Number of clusters/	Target - 22 clusters (est 600 households)
Target sample size	raiger - 22 clusiers (est our nousenous)
Primary outcome	Portions of FV eaten yesterday
Key secondary	Diet Quality, Food Insecurity, Long term health
outcomes	conditions
Process evaluation	To provide insight into the process of implementing the
	intervention, mechanisms of action of the intervention,
	and contextual factors which might impact the
	intervention.
Proposed Start and	1 st October 2021 - 1 st June 2022
•	
Date	

4. Introduction: the problem to be addressed

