4.3. Development and feasibility of the intervention

'Fresh Street' is an innovative multi-component intervention, which combines supplier specific vouchers for fresh FV with a range of diet and health information. The vouchers are offered to **all households** in a geographical area regardless of household type, size or income. The combination of fiscal measures with regular multi-faceted communication/ marketing information has been developed to reduce food insecurity, increase daily consumption of fresh FV, and improve dietary quality, support healthy dietary habits, and increase exposure to healthy food prompts.

In 2017, CR & MB & stakeholders developed and feasibility tested the 'Fresh Street' intervention in an area of high deprivation in the north of England funded by MRC PHIND, with support from Barnsley Metropolitan Borough Council and the Alexandra Rose Charity.

The feasibility of the scheme was assessed in four streets using rapid ethnographic assessment (Manderson et al, 1992) and voucher redemption information. The 12 month scheme was popular and seen to be of benefit to local people and local traders. Most (84%, 80/95) eligible households joined the scheme and most (89%) vouchers were redeemed. Householders frequently reported that the scheme made them think more about what they were eating, and prompted them to buy and eat more FV. The local FV shop and market stalls reported new customers and that existing customers were buying more. People frequently talked (unasked) about their health and some reported that the scheme motivated them to lose weight (Relton et al, 2020).

In 2018, a second feasibility test was conducted in a block of 54 two-bedroom flats in a deprived area of Sheffield ([name]). This was situated in a food desert (i.e.

no local supply of fresh FV). Vouchers were redeemable at the four FV stalls in Sheffield Moor Market (3 miles away), or exchanged for a £5 bag of fresh vegetables and apples delivered to the flats each week. About 75% of eligible households joined the scheme and 70%+ of the vouchers issued were redeemed. Doorstep conversations revealed similar responses to the Barnsley scheme (the scheme made them think more about what they were eating, and prompted them to buy and eat more FV) and market stalls reported new customers. However, interest in the weekly delivered £5 vegetable bag was low with most preferring to choose their own FV from the market stalls.

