The range of data that we plan to collect during the pilot is described in **Table 2. Data** collections tools and sources.

Surveys

Primary and secondary outcome data for the trial will be collected by contacting all households in the intervention and control clusters and asking one adult from each household to complete a survey. Collection of baseline data in the pilot will be completed before the introduction of the intervention.

If the decision is made not to progress to the main trial and/or the intervention ceases to be delivered then we will supplement baseline survey data with outcome survey data from households in all of the pilot clusters (objective j). We will use a repeated cross sectional trial design (i.e. the survey respondent from each household may not be the same at each data collection time point and respondents may also be from a different household if a new household moves into the house). This will enable us to obtain a representative picture for each of the streets.

The pilot will help us find ways to maximise survey responses (see section 7.8). We will find the best ways to frame questions (especially the primary outcome questions) by iteratively refining the script already developed. We will assess which questions need to be excluded from the survey either because householders perceive questions as irrelevant or sensitive e.g. ethnicity, vaccine status, or because the survey is too long.

Paper and/or online surveys

In the pilot we will begin with the paper survey. The research team will door knock every house in each of the streets and ask respondents to complete survey. If no one answers then the survey will be put through the letterbox with pen and stamp addressed envelope. After the first 200 households have had a chance to respond using the paper survey, if the response is insufficient (<50% provide baseline data) we will then introduce online surveys in addition to paper surveys. Using a cut-off of 200 responses will enable us to compare response rates and participant characteristics from paper and paper plus on-line surveys at the end of the pilot. After 200 responses the maximum margin of error around our assessment of response rate will be 7%.

If we collect data using both paper and on-line methods, then we need to decide whether one method gives a better representative sample than the other or whether to use both methods (and if so in what order/ time sequence).

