We aim to ensure that we obtain valid unbiased data (RoB 2 for cluster randomized trials) (see section 7.10). Surveys will only be valid if both the name of the street and the house number is provided. This will be the case for both paper and on-line surveys. If we receive two or more valid responses (paper or paper and online) from the same household, then we will consider the paper survey response as the primary response. If two or more valid online surveys are received then we will consider the first valid online response as primary if there is no paper response.

Questions in the paper and the online surveys will be exactly the same. Paper surveys will be branded for each site e.g. Tower Hamlets Food and Health Survey (see Appendix 1).

However, the online surveys come in three different formats and have the following names: "What do you eat?", "Do you have enough to eat?" and "Virus Health and Wellbeing checKer (V-HAWK)". (see Table 2)

These online surveys will be integrated into QMUL 'Healthy People, Healthy Places' online platform (https://qmul.citizenlab.co/en/).

		Online
Data item	Measure/ Source	survey
		name
Primary outcome data		
Portions of FV eaten yesterday	Active Lives Survey	What do you
	(two questions)	eat?
Secondary outcome data		
Diet Quality Score (in the past month)	Diet Quality	What do you
	Questionnaire (DQQ)	eat?
Food insecurity (in the previous 12 months)	Food Insecurity	Do you have
	Experience Scale	enough to
	(FIES)	eat?
Long term conditions (fatigue, pain,	Questions from the	Virus-Health
insomnia, anxiety, depression, diabetes,	Yorkshire Health Study	And
breathing problems, high blood pressure,	(YHS) Health	Wellbeing
heart disease, osteoarthritis, stroke, cancer,	Questionnaire	checKer (V-
long COVID, other)		HAWK)
Virus symptoms, COVID diagnosis		V-HAWK
Life satisfaction	YHS Health	V-HAWK
	Questionnaire	
Health Related Quality of Life	EQ-5D	V-HAWK
Healthcare utilisation (last 3 months)	YHS Health	V-HAWK
	Questionnaire	
Free text comments (diet and health)		What do you
		eat
		V-HAWK
Respondent and hous	sehold information	

Respondent Ethnicity, Age group, Gender, COVID vaccine status, Consent to contact. Household Composition Street name and house number

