Randomise clusters																						
Intervention delivery																						
Baseline & 4 month* data collection - paper surveys																						
Baseline & 4 month* data collection - online surveys																						
Data collection - interviews																						
Process evaluation																						
PILOT - NHS site																						
Randomise clusters																						
Intervention delivery																						
Baseline & 4 month* data collection - paper/online survey	5																					
Data collection - interviews																						
Process evaluation																						
Pilot data analysis																						
Seek additional intervention funding for main trial																						
Progression criteria review - NIHR & PSC																						
*Decide if 4 month data collection required																						
Write up final report OR proceed to main trial																						
NIHR reports																						

17. References

Curtis, L.A. and A. Burns (2018). Unit Costs of Health and Social Care 2018. DOI: https://doi.org/10.22024/UniKent/01.02.70995.

Department of Health (2005) Choosing a Better Diet: a Food and Health Action Plan http://webarchive.nationalarchives.gov.uk/+/www.dh.gov.uk/en/publicationsandstatistics/publications/publicationspublications/publi

Department of Health (2019). Healthy Start Voucher Take-up. NHS. https://www.healthystart.nhs.uk/healthy-start-uptake-data/. Accessed November 2019

Department of Work and Pensions (2019): DWP launches national measurement of household food insecurity press release. https://foodfoundation.org.uk/wp-content/uploads/2019/04/National-measurement-of-food-insecurity-release.pdf

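### If the conditional 4-month outcome survey is run, the 12-month food insecurity question would look back mostly over months before the vouchers and dilute any effect

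*Protocol*

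**What the plan says.** Table 2 in Protocol Section 7.9 gives the item as "Food insecurity (in the previous 12 months", measured with the Food Insecurity Experience Scale. Two neighbouring items have shorter windows: diet quality over the past month and healthcare use over the last 3 months.

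Food insecurity is not peripheral. The synopsis (Section 3) names the key secondary outcomes as "Diet Quality, Food Insecurity, Long term health" conditions. Section 7.9 places food insecurity second in a list ordered by how likely each outcome is to respond. Section 4.3 says the combined fiscal and information package "has been developed to reduce food insecurity", among other aims.

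On timing, the Section 16 timetable shows "Baseline & 4 month* data collection - paper surveys" for the non-NHS sites (with a matching online row) and "Baseline & 4 month* data collection - paper/online survey" for the NHS site. The asterisk leads to the row "Decide if 4 month data collection required". Section 7.9 gives the trigger: "If the decision is made not to progress to the main trial and/or the intervention ceases to be delivered then we will supplement baseline survey". The rest of that sentence provides for an outcome survey of households in every pilot cluster. The same section also says: "Collection of baseline data in the pilot will be completed before the introduction of the intervention". No later survey time and no shorter food insecurity window for follow-up appears anywhere in the protocol.

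**The concern.** A 12-month question asked 4 months after baseline reports mainly on the time before the scheme existed. A household that was food insecure only in the pre-voucher months would still correctly report it, however well the vouchers worked afterwards. No later analysis can separate the exposed months from the unexposed ones, because the answer is collected as one 12-month report. This is therefore fixed by the questionnaire and cannot be left to the SAP.

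At stake is the usefulness of one key secondary outcome in the situation where the pilot data would have to stand alone. Section 15 lists pilot data on effectiveness among the main outputs, intended to inform policy on food insecurity among other topics. A small or null difference on this item could be read as a failure of the scheme when it largely reflects the recall period.

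**Working it through.** The protocol gives no power, effect size or prevalence for food insecurity, so there is no figure of its own to reproduce.

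**Inputs from the protocol**
- Recall window R = 12 months (Section 7.9, Table 2).
- Follow-up F = 4 months (Section 16).
- Baseline completed before vouchers start (Section 7.9), so exposure at the 4-month survey is at most 4 months.

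**Share of the window before the vouchers**
- (R − F)/R = (12 − 4)/12 = 66.7%, leaving 33.3% exposed.
- This is a minimum. If the 4 months run from baseline and vouchers start a month later, it is (12 − 3)/12 = 75%.
- With recall of 4 months or less and 4 months of exposure, it is 0%. Keeping 12-month recall, it is 50% at a 6-month survey and reaches 0% only at 12 months.

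**Overlap with baseline**
- With vouchers starting at time 0, the baseline window runs from −12 to 0 and the follow-up window from −8 to +4. They share 8 months.

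**Illustration of the dilution**

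The following are assumptions that are not in the protocol: one yes/no outcome, meaning insecure in any month of the window; months independent and equally likely; 12-month prevalence p between 10% and 40%; vouchers abolish all food insecurity from day one.

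Prevalence still reported at 4 months = 1 − (1 − p)^(8/12). Relative fall = 1 − (reported prevalence)/p.
- p = 10%: reported 6.8%, fall 32%.
- p = 20%: reported 13.8%, fall 31%.
- p = 30%: reported 21.2%, fall 29%.
- p = 40%: reported 28.9%, fall 28%.

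The true fall in exposed months is 100% in every row. At the other extreme of persistence, where a household is insecure in every month or in none, the reported prevalence would not move and the visible fall would be 0%.

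Partial effects behave in the same way. With a constant monthly risk cut by 30% or 50% in exposed months, over the same prevalence range, the visible absolute difference is 30.5% to 33.0% of the difference a fully exposed window would show. At p = 20% and a 50% cut:
- Fully exposed: 0.20 − (1 − 0.8^(6/12)) = 9.4 percentage points.
- Exposed for 4 of 12 months: 0.20 − (1 − 0.8^(10/12)) = 3.0 percentage points.

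**The case against.** The strongest reply is that the mismatch may never arise. Objective j, Section 7.9, Section 7.11 and the timetable all make the 4-month survey conditional. If the study moves on to the main trial with the intervention still running, the pilot collects baseline data only, and a 12-month question at baseline is harmless. This stands and limits the point to the contingency branch. In that branch, however, the 4-month survey is the only outcome comparison the pilot makes. The baseline wording must also be settled before anyone knows whether the branch will be taken.

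A reader might infer that the item biases one arm against the other. The documents do not support that: Section 7.6 randomises streets within site, so pre-voucher experience balances in expectation. What remains is attenuation.

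A reader might also infer that the pilot could be stopped wrongly. Section 6.3 rests progression on baseline response and secured funding, and food insecurity plays no part. When non-progression triggers the survey, that decision has already been taken.

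The 22 clusters were not chosen to detect an effect on any outcome (Section 7.5), so a precise result was never promised. That is fair, but the dilution shrinks the estimate itself, apart from its precision.

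Finally, the pilot tests the survey for the main trial. Its follow-up time is not stated, and Section 6.3 seeks one or two years of intervention funding. A main-trial survey at 12 months or later would fit the current wording. That is a reason to keep a 12-month version available. It does not make that version suitable at 4 months.

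**Conclusion.** The point holds, conditionally. If the 4-month survey is run, at least 67% of the food insecurity recall window precedes the vouchers and 8 months of it repeat the baseline window. The result would understate any effect in the pilot's only outcome comparison. The 67% follows directly from the protocol's own figures. It assumes that the survey wording matches the Table 2 label, since the questionnaire in Appendix 1 was not available.

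The 28–32% visible fall is only an illustration. It depends on an assumed prevalence range, independent months and a yes/no outcome, whereas the instrument is a scale whose scoring the protocol does not give. Persistence from month to month would make the visible fall smaller.

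The documents do not support saying that the pilot would wrongly show no signal, or that the main trial shares the problem. This is an inexpensive improvement to one key secondary outcome. It is not a flaw in the trial's primary purpose.

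**What to change.** In Table 2 and in both the paper and online surveys, at baseline and at 4 months, ask food insecurity over a period no longer than the follow-up interval. The past month or the last 3 months would match windows already used for diet quality and healthcare use. The past month leaves more margin if vouchers start some time after baseline. Settle the wording before baseline collection begins. Section 7.13 already provides for agreeing changes to survey questions with those analysing the data.

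Keep the 12-month version at baseline if it is wanted for description, or for the main trial if follow-up there is 12 months or longer. If the 12-month item is kept alone, state in the protocol that the 4-month food insecurity result is descriptive and cannot be read as evidence of no effect.

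The cost is survey wording, plus either some loss of comparability with 12-month figures (and possibly with the main-trial item) or, if both versions are asked, a slightly longer survey section. The latter works against the aim in Section 7.8 of keeping the survey short.

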7.10. Sources of data relating to the intervention

Types and sources of data relating to the intervention are listed in Table 3. This includes data on the delivery of the intervention (voucher data), FV supply data from vendors and also opportunistic conversations with householders and FV retailers.

Voucher distribution and redemption data will enable us to identify which households have redeemed vouchers, where and when. This will also enable us to cease supply of vouchers to households not using the vouchers. Households will be informed that if they do not use the vouchers within 4 - 6 weeks of receipt then we will stop delivering the weekly envelopes (which contain the vouchers). The rationale for this is two-fold (i) to prompt householders to use the vouchers regularly (rather than stockpile and/or trade/sell on) and (ii) unused vouchers create waste and increase the cost of the intervention. However, retailers will be told to accept all vouchers regardless of use by date so that it is easy for the retailers to rapidly accept the vouchers.

Some FV stalls and FV shops may sell non FV items. We will explore the extent of any vouchers being used to purchase non FV items (i.e., 'trade' in vouchers) during qualitative interviews with local residents and by using 'mystery shoppers' (Jumbe et al, 2019) (see section 7.15). FV retailers are made aware of the possibility of a visit by mystery shoppers on sign up. Mystery shoppers will also periodically collect data on prices of key FV products at local participating and non-participating FV retailers, to study any possible effects of the intervention on FV prices over the lifespan of the pilot and the impact of changing prices on the use of vouchers. Information on the types of FV items purchased will be collected during opportunistic conversations with householders and FV retailers e.g. during delivery of envelopes or checking with FV retailers on how the scheme is working.

Intervention delivery data									
Type of data	Source								
Vouchers distributed (date, household)	Log data								
Vouchers redeemed (date, location)	Voucher Reimbursement system								
Resources required to distribute and	Study records								
redeem vouchers									
Items purchased (including any 'trade' in	Mystery shoppers, Opportunistic								
vouchers	conversations with vendors, householders								
FV price data	Mystery shoppers								

Table 3: Data on the intervention

Trained local community researchers will conduct doorstep conversations and one to one interviews, either in person or remotely, with a maximum variety, purposive, sample of householders. An experienced qualitative researcher will conduct informal interviews with local opinion leaders and stakeholders including commissioners, LA employees, local PH

staff, and FV retailers. Qualitative data, such as that inputted in the free text sections of the surveys and the data gathered through interviews and doorstep conversations, will be analyzed using content and thematic analyses. This form of analysis will enable us to identify prominent topics and key themes across the data sets collected.

7.11. Methods to reduce potential bias in outcome measurement.

Randomisation guards against much of the bias between groups in outcome measurement. However, in trials such as Fresh Street where participants providing data and/or outcome assessors are not blinded to the intervention, bias in those responding and their responses can occur. When high response rates are achieved the effect of bias in those responding is minimised. When response rates are lower there is more potential for this bias. In the pilot we are not collecting outcome data unless the pilot indicates that the main trial is not feasible; thus if the main trial goes ahead we will have no direct information on these biases prior to starting the main trial. We can, however, explore what participants say about what might affect their likelihood of responding and likelihood of responding in certain ways within the qualitative part of the pilot study.

We will take care that intervention messaging around FV consumption does not bias survey responses from the intervention group. We also plan to match intervention and control streets and collect outcome data in matched streets at the same time to ensure no differences in the mode or time of when surveys are delivered/ collected to intervention and control.

Bias in responders will occur if there are differences between responders in the intervention and control group in relation to (1) factors that are known or thought to affect the primary outcome - self-reported fruit and vegetable consumption (2) factors that might affect the uptake of the intervention.

Factors known or thought to affect fruit and vegetable consumption are mainly related to socio economic status (SEC). Data on proxy markers for SEC will be collected in the pilot study (ethnicity, health related quality of life, long term conditions and multi-morbidity). Factors that might affect the uptake of the intervention will be assessed in the pilot (e.g. Household composition). Table 4 below describes the data collected to help the pilot evaluation and includes the rationale for collecting each type of data.

Rationale for data sought	Type of data included
Primary outcome measure	Portions of FV eaten yesterday (two Active Lives
	Survey questions)
Secondary outcome measures	Diet Quality Questionnaire (DQQ), Food insecurity,
	Long Term Health conditions, Virus symptoms,
	COVID diagnosis, life satisfaction, EQ-5D
To ensure unique response from each	House number, Street name
included household and to enable outcome	
analyses to adjust correctly for clustering	
To enable subgroup analyses (especially	Household composition (numbers in household,
comparison with DH funded Healthy Start	under 5 yrs, 5-18 yrs, 65yrs+)
Scheme)	

Table 4: Survey evaluation data

To understand characteristics of survey responders and help assess whether intervention and control group responders are similar/balanced	Ethnicity, EQ-5D, Long Term Health conditions, multi-morbidity, Household type; age and gender
Other types of data collected	
General information	Free text "any comments about your diet" question
Process data (paper)	Date survey distributed/ returned
	Whether accept voucher or not
	Doorstep conversation data
Process data (online)	Date survey distributed/ returned
	IP address

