7.4. Intervention

The intervention (Fresh Street scheme) is described below using the Template for Intervention Description and Replication (TIDieR) checklist (Hoffmann et al, 2014). The pilot will enable us to deliver the intervention in different sites (objective a), assess uptake and identify factors which may impact on intervention success (objective b), create a manual describing a potential new public health intervention (Fresh Street) (objective c), (see Section 7.9 Data collection) and improve our ability to evaluate the intervention in the main trial (objectives d & f).

Item 1. Brief name : Provide the name or a phrase that describes the intervention	Fresh Street A place-based household voucher approach to increasing fruit and vegetable consumption.
Item 2. Why: Describe any rationale, theory, or goal of the elements essential to the intervention	The Fresh Street combination of fiscal measures with regular multi-faceted communication/ marketing information is designed to reduce food insecurity, increase daily consumption of fresh FV, and improve dietary quality, support healthy dietary habits, increase exposure to healthy food prompts. The goal is to help re-orientate local food systems so that they support healthy eating patterns, and advance the economic, social and environmental goals which impact on health in the longer term.
Item 3. What (materials): Describe any physical or informational materials used in the intervention, including those provided to participants or used in intervention delivery or in training of intervention providers.	Intervention materials delivered weekly in branded envelopes to individual households. Each envelope contains a letter to households with £5 worth of Fresh Street branded paper vouchers redeemable with local independent FV retailers (not supermarkets), a healthy and seasonal vegetable based recipe and nutrition and health/diet related information. Letters may include additional content e.g. encouraging households to share unused vouchers. A branded website offers online information. Branded posters displayed at participating FV retail outlets to show they accept Fresh Street vouchers.

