Item 4. What (procedures): Describe each of the procedures, activities, and/or processes used in the intervention, including any enabling or support activities	Printing of secure, traceable, vouchers by A1 Security Print https://www.a1securityprint.com/ , redeemable at local FV retailers Training of FV retailers (what items vouchers can be used for and how to redeem the vouchers) Writing weekly covering letters Printing letters and packing envelopes and delivering envelopes

Table 1: Intervention description using the TIDieR checklist

	FV shopping and spending of vouchers by participants Redemption of vouchers by FV retailers, scanning unique QR codes using online app developed by A1 Security Print Reimbursement of voucher value
Item 5. Who provides : For each category of intervention provider (for example, psychologist, nursing	A1 Security Print have expertise in the production of secure cash transfer processes. Their clients include retail, education, government and banking.
assistant), describe their expertise, background and any specific training given	Local council staff bring their understanding of socio- economic conditions and public health issues in their local areas supplemented by the experience gained by QMUL staff in previous Fresh Street feasibility studies.
	FV retailers engage with households (customers) and are experts in the supply and use of FV in each local area.
	Community partners recruited to facilitate the weekly delivery of envelopes. This will involve local community and charity groups e.g. Good Gym (www.goodgym.org) a social enterprise which engages in community activities.
Item 6. How: Describe the	Envelopes delivered by hand by community partners or local
modes of delivery (such as face to face or by some other	staff.
mechanism, such as internet	FV picked up by participants or delivered to their door
or telephone) of the	
intervention	
Item 7. Where: Describe the	Fresh Street is designed to be delivered in areas of high
type(s) of location(s) where the intervention occurs,	deprivation (IMD deciles 1-4) and low fruit and vegetable consumption.
including any necessary	Fresh Street vouchers delivered by hand to households in
infrastructure or relevant	participating streets.
features	Fresh FV supplied by local market traders either in their own
	premises or through their existing delivery channels.
Item 8. When and how	Households receive the intervention (including vouchers

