7.14. Data analysis

Analysis of voucher distribution and redemption data will enable us to assess uptake of the intervention (objective b) including weekly spending patterns of each household - how many vouchers were spent, and when and where.

We will assess what proportion of households contacted provide valid baseline primary outcome measure responses (objective e).

Any analysis of outcome data will be by intention-to-treat. All clusters and households for whom an outcome is available will be analysed according to the group to which they were randomised. Households which cannot be linked to a street participating in the study will be excluded.

The primary outcome analysis will compare the mean difference between intervention and control in portions of FV eaten the day before. A mixed regression model will be used where an individual household outcome at follow-up is adjusted for baseline cluster (street) mean score and site, and within cluster correlation is allowed for.

There is likely to be some contamination relating to sharing of vouchers, sharing of information, supplier effects and household churn i.e. households moving into or out of the intervention/ control streets. Potential sources of contamination will be monitored throughout during qualitative interviews and analyses adjusted where possible.

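### Letters may encourage households to share unused vouchers with anyone, and the redemption data then credit a shared voucher to the household it was sent to

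*Protocol*

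**What the plan says.** Four parts of the protocol bear on this.

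- **Stop rule and its basis (section 7.10).** The protocol states that "Voucher distribution and redemption data will enable us to identify which households have redeemed vouchers, where and when". Supply ends for non-users: households are told that "if they do not use the vouchers within 4 - 6 weeks of receipt then we will stop delivering the weekly envelopes". One reason given is "to prompt householders to use the vouchers regularly (rather than stockpile and/or trade/sell on"); the other is to avoid the waste and cost of unused vouchers.
- **What is recorded (Table 3 and Table 1 Item 4).** At issue the log holds "Vouchers distributed (date, household"). At redemption the system holds "Vouchers redeemed (date, location"), captured by retailers "scanning unique QR codes using online app".
- **Sharing (Table 1 Item 3).** "Letters may include additional content e.g. encouraging households to share unused vouchers". No recipient is specified.
- **Use of the data (section 7.14).** Uptake (objective b) is to be assessed from the voucher data, "including weekly spending patterns of each household - how many vouchers were spent, and when and where". The same section expects some contamination through voucher sharing, to be monitored in qualitative interviews, with adjustment where possible.

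Section 7.6 adds that streets are randomised within an area of 500 to 1200 households chosen by the council at each site.

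**The concern.** The QR code identifies a voucher, and the log says which household that voucher was sent to. Nothing listed identifies the person who spent it. While vouchers stay with the household they were sent to, redemption by that voucher's code is a fair stand-in for household use. Once vouchers change hands it is not, and Item 3 allows the trial's own letters to encourage that.

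Two things are at stake. The first is the meaning of the uptake measure. Uptake is a pilot objective and feeds the intervention manual (objective c), and some households that do not use the scheme would be recorded as regular users and would escape the stop rule. The second is where shared vouchers go. Nothing in Item 3 keeps them out of control streets in the same area, so a letter could encourage what section 7.14 lists as contamination.

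**Working it through.** The protocol gives no sharing rate and no figure for its effect, so there is no stated number to reproduce. The check is a reading of the records, followed by illustrations on assumed rates.

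**1. What the records can show.** The only route from a redemption to a household is: QR code, then voucher, then household of issue. Suppose household A gives a voucher to household B, which spends it. The record shows A's voucher redeemed on a date at a location. A counts as a user, A's envelopes continue, and B's use is not recorded. The statement in section 7.10 about which households redeemed vouchers therefore holds only if vouchers do not change hands.

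**2. Household uptake (assumed rates).** Let n be the number per 100 supplied households that do not use their own vouchers, and h the proportion of those that pass on at least one voucher that is redeemed. Overstatement = n × h points.

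| n | h = 0 | h = 0.25 | h = 0.50 |
|---|---|---|---|
| 10 | 0 | 2.5 | 5 |
| 20 | 0 | 5 | 10 |

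**3. Vouchers spent (assumed rates).** Section 4.3 reports 89% redemption in the first feasibility test. If a share t of redeemed vouchers were spent by another household, own-household use would be 0.89 × (1 − t): 84.6% at t = 5%, 80.1% at t = 10% and 71.2% at t = 20%. At t = 0 it stays at 89%.

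**4. Contrast between arms.** Let s be the share of vouchers their own household would leave unused, and c the share of those that would reach control streets, the rest staying in intervention streets. Take equal arms and an effect proportional to vouchers spent, with 1 as the contrast if every voucher is spent in the intervention arm.

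- No sharing: the unused vouchers have no effect, so the contrast is 1 − s.
- Unrestricted sharing: the intervention arm spends 1 − sc and the control arm sc, so the contrast is 1 − 2sc.
- Own-street message, with vouchers that would have gone to control streets left unspent: 1 − sc.
- Own-street message, with all of them spent within the street: 1.

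| s, c | No sharing | Unrestricted | Own street, rest unspent | Own street, all spent |
|---|---|---|---|---|
| 0.05, 0.25 | 0.95 | 0.975 | 0.9875 | 1 |
| 0.20, 0.25 | 0.80 | 0.90 | 0.95 | 1 |
| 0.20, 0.50 | 0.80 | 0.80 | 0.90 | 1 |

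Since 1 − 2sc ≥ 1 − s whenever c ≤ 0.5, unrestricted sharing of vouchers that would otherwise go unused does not lower the contrast in that range. Above c = 0.5 it does. The own-street wording is at least as good as unrestricted sharing in every case, because 1 − sc ≥ 1 − 2sc.

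**The case against.** The strongest reply is that the protocol does not contradict itself. The stop rule is aimed at stockpiling, trading and selling on, and at waste. Giving an unused voucher to a neighbour is none of the first three and reduces the fourth. The sharing text is optional. Not knowing the bearer is inherent in paper vouchers, and section 7.14 already recognises sharing. Apart from the interviews (up to 15 intervention and up to 6 control householders), the protocol lists doorstep and opportunistic conversations, vendor interviews and auditable vouchers.

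Most of this stands. There is no textual contradiction between the stop rule and the letters, and a missing bearer field is not a fault in itself. What the reply leaves open is the statement that the data identify which households redeemed vouchers, and the uptake analysis built on it. The interview sample is purposive, and none of the other sources is given a fixed question on sharing, so nothing listed yields a quantity with which to correct household-level uptake. Nor does the reply explain why a sharing message should be free to reach control streets.

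A reader might go further and infer that the letters dilute the planned 0.5-portion difference, so that the original main-trial figure of 856 households per arm must rise. The documents do not support this. That inference takes as its baseline a donor who would have spent every shared voucher, whereas Item 3 concerns unused ones. Against the right baseline, 1 − s, unrestricted sharing leaves the contrast equal or larger for c up to 0.5. Deleting the message would therefore not raise the contrast in that range. Section 7.5 also says the main-trial size may be recalculated.

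**Conclusion.** The point holds as a limited, inexpensive improvement. Once vouchers are shared, household use is overstated and the stop rule misses non-users who pass vouchers on. A sharing message with no limit on recipients also lets vouchers cross into control streets when they need not.

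The true size is unknown. The 2.5 to 10 points for household uptake, and the fall from 89% to between 84.6% and 71.2% for vouchers spent, rest wholly on assumed rates and are zero if nobody shares. The attribution gap does not depend on the letter, since section 7.14 expects sharing anyway; the letter would add to it.

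The progression criteria concern baseline response and funding and are unaffected. So is analysis by randomised group. Any effect on the outcome contrast matters only if 4-month data are collected, which section 7.9 makes conditional on the main trial not going ahead or delivery ceasing, or if the letters carry over to the main trial.

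**What to change.** - **Table 1 Item 3:** if a sharing message is used, word it so that unused vouchers go only to neighbours in the same street. The street is the unit of randomisation, so those neighbours have the same allocation.
- **Sections 7.10 and 7.14:** define and report uptake as redemption of vouchers sent to a household, and state that this does not show use by that household. Describe the stop rule in the same terms: it acts on vouchers sent to a household and not redeemed.

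The cost is a few lines of text. Vouchers, log, randomisation and survey stay as they are. A few unused vouchers may go unredeemed that would otherwise have been passed further afield, and the uptake measure is described more modestly. I would not add a survey question on vouchers received from others: it would name the scheme to control households and lengthen a survey that section 7.8 aims to keep short.
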